8.6. Data management

The data will be analyzed using the statistical package program. The categorical variables will be given as number and percentages, and the continuous variables will be presented as averages and standard deviations. For between-group comparisons of categorical variables, the chi-square test will be used. The continuous variables will be tested for normal distribution using the Kolmogorov-Smirnov test and the Shapiro Wilks test. For the normally distributed continuous variables, the parametric tests (the t-test, the ANOVA, the repeated measures analysis of variance, etc.), and for the continuous variables without a normal distribution, the non-parametric tests (the Mann-Whitney U test, the Kruskal Wallis analysis of variance, the Friedman Analysis of Variance, etc.) will be used. The level of significance will be taken as $p = 0.05$.

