7. RESEARCH QUESTION AND OBJECTIVES

Research Question:

In this study, different from other studies in the literature, the data will be collected to observe the quality of life and efficacy after first line interferon alpha and second line TKI treatments.

Primary Objective:

- Measurement of health-related quality of life with targeted therapy used as 3rd line.
- Overall response rate at the end of follow up
- Median progression free survival according to RECIST version 1.1

Secondary Objectives:

- Overall survival rate
- Effect of quality of life on prognosis.
- Adverse events during 3rd line targeted treatment according to CTCAE.4.03
- Dose modifications due to adverse events
- Correlation between efficacy (overall response rate at month 12 and median PFS) and dose modifications due to adverse events
- Correlation between efficacy (overall response rate at month 12 and median PFS) and blood pressure

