8. RESEARCH METHODS

8.1. Study design

This is a multi-center post-marketing observational study. It has been defined according to the NUTS (Nomenclature of Territorial Units for Statistics: Nomenclature d'unités Territoriales Statistiques, French) criteria, which is a regional classification, created in order to reduce interregional disparities in socio-economic analysis of the regions, and to produce data comparable to that of the European Union (EU). Turkey has been divided into 12 NUTS regions depending on the economic, social, cultural, and geographical aspects, and the population size. In this study, patients with metastatic renal cell carcinoma from centers in 12 NUTS regions of Turkey will be included, who meet the inclusion criteria. Since this is a non-interventional observational study, there is no specific follow-up protocol. In this study, approximately 152 patients planned to be recruited in a year and followed-up 12 months.

This is a multi-center post-marketing observational study. In this study, patients with metastatic renal cell carcinoma from centers in 12 NUTS regions of Turkey will be included,

who meet the inclusion criteria. Since this is a non-interventional observational study, there is no specific follow-up protocol.

Presuming that there are 1800 patients with metastatic renal carcinoma in Turkey, the minimum sample size was calculated as 152.

There will be a total of 25 centers in various cities of Turkey.

The centers will consist of medical oncology clinics.

In this study, the patient follow-up period is 12 months. Each patient will be followed up to 5 times; the data will be collected at baseline, the 3rd, 6th, 9th and 12th months according to the routine practice. Additionally, every patient will be followed-up once for survival follow-up in order to assess the overall survival before the site close out visit. Survival follow-up will be performed via telephone visit or site visit if exist.

Because of the observational nature of the study, there is no predefined treatment protocol. The participating physician will continue to treat the patients at his/her own discretion. Frequency of visits will be continued per physician's preference.

The patients will be asked to fill in the quality of life questionnaire (FKSI-15, EQ5D-3L, FKSI-DRS) on each visit.

The assessment of the side effects will be based on the "Common Terminology Criteria for Adverse Events". The CTCAE V.4.03 will be used.

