Outcome Measures are overall objective response rate (ORR) [Time frame: from enrollment to objective response], progression-free survival (PFS) [Time frame: from enrollment to disease progression or death, whichever occurs first], overall survival (OS) [Time frame: from enrollment to death or the end of the study duration] and probability of patient survival at 1 year [Time frame: from enrollment to 1 year]

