8.3. Variables

The outcome variables for the objective(s) are time to treatment failure (from start of treatment to progression or permanent discontinuation), overall survival (from start of treatment to the date of last follow up or death), therapeutic response to therapy based on response evaluation criteria in solid tumors (RECIST version 1.1), and safety (type, incidence, severity of adverse events graded by the National Cancer Institute [NCI] CTCAE V.4.03)

Variable	Role	Data source(s)	Operational definition
Age, gender, height, weight, blood pressure, socio-demographic characteristics	Baseline characteristic	Medical Records	
Concomitant diseases	Baseline Characteristic	Medical Records	
Medication	Baseline Characteristic	Medical Records	
Histopathological findings	Baseline Characteristic	Medical Records / Pathology Reports	
Surgical Operations	Baseline Characteristic	Medical Records	
The cytokine (interferon alpha) usage in the first-line treatment, TKI usage in the 2 nd line treatment and the dosage and the duration of the treatment	Baseline Characteristic	Medical Records	
Metastatic features	Baseline Characteristic	Medical Records	
MSKCC risk factors	Baseline Characteristic Follow-up Characteristic	Medical Records	
3 rd line treatment	Baseline Characteristic Follow-up Characteristic	Medical Records	

	Close-out Characteristic		
The performance score before the second and third-line treatment		Medical Records	
The quality of life questionnaire (FKSI-15, EQ5D-3L, FKSI-DRS) on each visit	Baseline Characteristic Follow-up Characteristic Close –out Characteristic	Patient interview	
Blood pressure		Patient diary	
Other treatment during follow-up, if any, the dose and the duration	Follow-up Characteristic	Medical Records	
Treatment of the side effects, interruption of the treatment, dose reduction, dose-elevation	Baseline Characteristic Follow-up Characteristic	Medical Records	
Duration of PFS, OS and ORR	Follow-up Characteristic Close-out Characteristic	Medical Records	

Schedule Procedure	Initial visit	Follow-up 3.month	Follow-up 6.month	Follow-up 9.month	Follow-up 12.month	Survival Follow-up
Demographic data	X					
Histopathological Findigs	X					
Medical history	X					
Previous therapy of mRCC	X					
MSKCC Risk Factors	X	X	X	X	X	
Surgical Operations	X					
Metastases Information	X					
FKSI-15, EQ5D-3L, FKSI-DRS Questionnaire	X	X	X	X	X	
Evaluation of PFS,OS and ORR		X	X	X	X	
Concomitant medication	X	X	X	X	X	
Visit date	X	X	X	X	X	

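### Quality of life, the first primary objective, has no assigned analysis; the repeated-measures tests in 8.6 would use only patients with all five forms, and visit averages alone do not show within-patient change

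*Combined protocol and SAP*

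**What the plan says.** Section 7 puts "Measurement of health-related quality of life with targeted therapy used as 3rd line" first among the primary objectives. The instruments are FKSI-15, FKSI-DRS and EQ5D-3L. Section 8.1 states that "the data will be collected at baseline, the 3rd, 6th, 9th and 12th months according to the routine practice", and adds: "Frequency of visits will be continued per physician's preference". The schedule in 8.3 shows the questionnaires at the initial visit and the four follow-ups.

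The outcome definitions leave quality of life out. The list in 8.1 opens with "Outcome Measures are overall objective response rate (ORR" and goes on to PFS, overall survival and 1-year survival. The sentence in 8.3 begins "The outcome variables for the objective(s) are time to treatment failure" and continues with survival, tumour response and safety. The questionnaires appear in 8.3 only in the variable table and the schedule.

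Section 8.6 gives generic rules tied to no endpoint. It says "the continuous variables will be presented as averages and standard deviations", then, for normally distributed variables, "the parametric tests (the t-test, the ANOVA, the repeated measures analysis of variance, etc". Friedman is among the non-parametric counterparts, and both lists are open-ended.

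Section 8.7 and the abstract assign summaries to demographics, time-to-event variables, treatment duration, tumour status by visit, physician-rated efficacy, adverse events, tolerability and best response. Quality of life is not among them. The two analysis sets are defined by adverse-event and efficacy information, not by questionnaires. Section 8.8 has missing data completed, commented on or queried. Section 8.7 defers permitted data modifications to a Data Management Plan that is not part of these documents. Sections 8.5 and 8.7 describe a study without a hypothesis and mainly descriptive.

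**The concern.** A primary objective needs a stated score, population, time point and rule for missing forms. Here none is given, so the defaults in 8.6 decide.

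Those defaults treat patients who leave in two different ways. A classical repeated-measures ANOVA or Friedman test drops anyone with a single missing form. Averages by visit, if that is how 8.6 is applied, use a different set of patients at each visit. In third-line metastatic disease, with withdrawal allowed at any time (9.2), forms will be lost through death as well as non-completion, and queries cannot recover them. A reader shown a flat line of averages could not tell stable quality of life from the loss of patients with worse scores unless the numbers alive and completing were printed beside it.

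**Working it through.** **The plan's own figure.** Assuming p = 0.5, the 152 in 8.5 is the precision of one proportion: n0 = 1.96² × 0.25 / 0.076² = 166.3. With a population of 1800, n = 166.3 / (1 + 165.3/1800) = 152.3. It reproduces, but uses no quality-of-life input.

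**Patients with all five forms.** The documents give neither retention S at 12 months nor completion c per visit. Assume S = 0.4 to 0.8 and c = 0.85 to 0.95. The count is 152 × S × c⁵, with 0.85⁵ = 0.444 and 0.95⁵ = 0.774:
- S = 0.4: 27 to 47
- S = 0.6: 40 to 71
- S = 0.8: 54 to 94

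If the first form is always complete, c⁴ replaces c⁵ and the overall range is 32 to 99. The share of collected forms used is 5 × S × c⁴ / (sum of S^(k/4), k = 0 to 4). At the low end this is 5 × 0.4 × 0.522 / 3.331 = 0.31; at the high end, 5 × 0.8 × 0.815 / 4.486 = 0.73.

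**Simulated trend.** All inputs are assumed, in baseline SD units: intercept SD 0.8, residual SD 0.6, 12-month change -0.48 with slope SD 0.3 or 0.5, and 120,000 patients per scenario. Leaving depends on the last observed score, by a given log-odds per SD worse. The 12-month difference in visit means was:

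| Retention | No dependence | Log-odds 0.5 | Log-odds 1.0 |
|---|---|---|---|
| 40% | -0.47 to -0.49 | -0.20 to -0.24 | -0.02 to -0.07 |
| 60% | -0.47 to -0.49 | -0.31 to -0.33 | -0.19 to -0.22 |
| 80% | -0.47 to -0.49 | -0.41 | -0.34 to -0.35 |

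A mixed model (visit as category, unstructured covariance) gave -0.47 to -0.49 throughout. The visit means matched the true mean of patients still in the study within about 0.01, so each is right for the patients it describes.

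**Complete cases, same simulation.** Change was -0.47 to -0.51, about right. The baseline mean was too high by 0.07-0.29 SD (log-odds 0.5) or 0.13-0.47 SD (log-odds 1.0). With a more variable slope (slope SD 0.8, intercept SD 0.9, residual SD 0.44), complete-case change was -0.35 to -0.46 and the mixed model -0.47 to -0.49.

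**Precision** (n = 152, 90% completion, log-odds 0.5 or 1.0). Standard error of change, complete case over mixed model:
- Month 6: from 0.103/0.081 = 1.27 to 0.150/0.093 = 1.61
- Month 12: from 0.151/0.132 = 1.14 to 0.155/0.114 = 1.36

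From unrounded values the excess is 28-62% and 14-35%. Over 85-95% completion it widens to 16-82% and 7-51%.

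**Leaving by an unobserved slope.** Visit means and complete cases gave -0.18 to -0.45 and the mixed model -0.23 to -0.45, so little is corrected. A hand check under a similar mechanism: true change -0.50, SD of change 0.5, correlation 0.5 between change and staying, half the patients kept. The mean change among those kept is -0.50 + 0.5 × 0.5 × 0.798 = -0.30. With zero correlation it stays at -0.50.

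**The case against.** The other side has a good deal. The study is descriptive, and the open-ended lists in 8.6 permit a mixed model. The unseen Data Management Plan may hold missing-data rules. Visit averages are correct for patients alive and completing the form. The simulation has one exit process and does not separate death from live dropout. If leaving is death, -0.48 is the mean had nobody died, which nothing in the documents makes the target. Complete-case change is about right under the main variances, and the mixed model does well largely because leaving was made to depend on observed scores.

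All of this stands, and it limits the size of the point. It does not supply an analysis. Permission to use a method is not assignment, and 8.7 gives the Data Management Plan patient validity, consistency checks and data modifications, not endpoint analyses.

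A reader might infer that the plan will report falsely stable quality of life. The documents do not support that. By-visit averaging is not stated for these scores (8.7 mentions visits only for tumour status). No attrition figures are given, and the link with outcome appears only as a secondary question, "Effect of quality of life on prognosis". Nor do they support calling repeated-measures ANOVA biased for change: that arises only with widely varying slopes or leaving driven by unobserved decline.

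**Conclusion.** The gap in the text is certain: the first primary objective has no assigned analysis, and only the generic rules of 8.6 reach it. It should be closed, but it does not invalidate the study.

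Its consequences are conditional. If repeated-measures ANOVA or Friedman is used in classical form, 27 to 94 of 152 patients contribute. Precision falls (standard error roughly 30-60% larger at month 6 and 15-35% at month 12, at 90% completion and with leaving related to scores), and the group described has better baseline scores. If averages are taken by visit, they are right for patients alive and completing, but their trend can understate within-patient decline if patients with worse scores leave earlier. Without that dependence there is no distortion.

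Retention, completion, variances and dependence are all assumed. A mixed-model mean should not be read as quality of life while alive, since after death it is hypothetical.

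**What to change.** In 8.6/8.7, assign the analysis for FKSI-15, FKSI-DRS and one named EQ5D-3L score (index or VAS):
- Replace repeated-measures ANOVA/Friedman for these scores with a linear mixed model for repeated measures, visit as category. Use all available questionnaires from patients with at least one dose of third-line treatment and at least one form.
- Report the mean and the change from the enrolment visit with 95% CI; no test is needed. Say that this visit may follow up to one month of treatment (8.2.1), so it is not a pre-treatment baseline.
- Keep averages and SDs by visit as the description of patients alive and completing. Print numbers alive and numbers completing beside each, so that death is separated from non-completion.
- Show mean profiles by time of last questionnaire or death.
- Label the mixed-model mean as hypothetical after death.
- Assign forms to visits by window, since timing follows routine practice, and state whether forms completed after third-line therapy ends are included.

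The cost is a paragraph of text and modest programming; no data are needed beyond the planned questionnaires and survival status. The drawback is that the model corrects little if leaving depends on decline not seen in the observed scores. Against complete cases the gain in month-12 change is mainly precision; against visit means it is a trend not distorted by leaving that depends on observed scores.

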8.7. Data analysis

Statistical analyses will be primarily of explorative and descriptive nature. All issues concerning patient validity, data consistency checks, permissible data modifications will be described in detail in the Data Management Plan.

Patients who took at least one dose of 3rd line treatment and have sufficient information whether they had an adverse event or not will be valid for safety analysis. Patients who took at least one dose of 3rd line treatment and have any information regarding efficacy of 3rd line treatment will be valid for intent-to-treat efficacy analysis.

Demographic data, baseline characteristics, diagnosis and prior treatment of RCC, concomitant diseases, and concomitant medication will be described with summary statistics such as mean, SD, minimum, 1, 5, 25, 75, 95, 99 percent quartiles, median, maximum for continuous variables, and category counts and frequencies (percentages) for

categorical variables. Concomitant diseases on the case report form correspond to MedDRA terms. Concomitant medication will be coded using WHO's drug dictionary.

Descriptive summaries of Kaplan-Meier (KM) estimates (including number of failed, number censored, 25th and 75th percentiles with respective 95% confidence level and median with 95% confidence level) and KM curves will be presented for time-to-event efficacy variables (PFS, TTP, time to treatment failure). Mean, SD, minimum, 1, 5, 25, 75, 95, 99 percent quartiles, median, maximum will be produced for duration of TKI treatment. Category counts and frequencies (percentages) will be calculated for tumor status at different visits and general subjective rating of efficacy of TKI from the treating physician.

Adverse events will be summarized using the MedDRA and the CTCAE coding system. Event rates for single adverse events will be calculated based on the total number of patients valid for safety. Adverse events will be categorized according to relation, seriousness, CTCAE grade (version 4.03), and discontinuation of therapy, action taken and outcome. Serious adverse events and unexpected or unlisted ADRs will be evaluated separately.

Category counts and frequencies (percentages) will be calculated for overall tolerability.

The factors, which might have impacted the duration of treatment, will be studied by retrospectively.

The best overall response is the best response recorded from the start of the study treatment until the end of treatment taking into account any requirement for confirmation. On occasion a response may not be documented until after the end of therapy so protocols should be clear if post-treatment assessments are to be considered in determination of best overall response. Protocols must specify how any new therapy introduced before progression will affect best response designation. The patient's best overall response assignment will depend on the findings of both target and non-target disease and will also take into consideration the appearance of new lesions.

8.8. Quality control

Data will be captured with e-CRF. Missing data should be completed or commented upon by the physician. After data checked, missing or implausible data will be queried. A check for multiple documented patients will be done. The data will be verified by an error analysis. Finally source data verification will be conducted in all of patients, 100% SDV will be performed. All investigators will be sufficiently trained for participation in the study.

To enable evaluations and/or audits from regulatory authorities or Pfizer, the investigator agrees to keep records, including the identity of all participating patients (sufficient information to link records, e.g., CRFs and hospital records), all original signed informed consent forms, copies of all CRFs, serious adverse event forms, source documents, and detailed records of treatment disposition, and adequate documentation of relevant correspondence (e.g., letters, meeting minutes, telephone calls reports). The records should be retained by the investigator according to local regulations, or as specified in the Clinical Study Agreement, whichever is longer.

If the investigator becomes unable for any reason to continue to retain study records for the required period (e.g., retirement, relocation), Pfizer should be prospectively notified.

The study records must be transferred to a designee acceptable to Pfizer, such as another investigator, another institution, or to an independent third party arranged by Pfizer. The investigator must obtain Pfizer's written permission before disposing of any records, even if retention requirements have been met.

8.9. Other aspects

Not applicable.

9. PROTECTION OF HUMAN SUBJECTS

9.1. Patient Information and Consent

All parties will ensure protection of patient personal data and will not include patient names on any sponsor forms, reports, publications, or in any other disclosures, except where required by laws. In case of data transfer, Pfizer will maintain high standards of confidentiality and protection of patient personal data.

The informed consent form must be in compliance with local regulatory requirements and legal requirements.

The informed consent form used in this study, and any changes made during the course of the study, must be prospectively approved by both the IRB/IEC and Pfizer before use.

The investigator must ensure that each study patient, or his/her legally acceptable representative, is fully informed about the nature and objectives of the study and possible risks associated with participation. The investigator, or a person designated by the investigator, will obtain written informed consent from each patient or the patient's legally acceptable representative before any study-specific activity is performed. The investigator will retain the original of each patient's signed consent form.

9.2. Patient withdrawal

Patients may withdraw from the study at any time at their own request, or they may be withdrawn at any time at the discretion of the investigator or sponsor for safety, behavioral, or administrative reasons. In any circumstance, every effort should be made to document subject outcome, if possible. The investigator should inquire about the reason for withdrawal and follow-up with the subject regarding any unresolved adverse events.

If the patient withdraws from the study, and also withdraws consent for disclosure of future information, no further evaluations should be performed, and no additional data should be collected. The sponsor may retain and continue to use any data collected before such withdrawal of consent.

9.3. Institutional Review Board (IRB)/Independent Ethics Committee (IEC)

It is the responsibility of the investigator to have prospective approval of the study protocol, protocol amendments, and informed consent forms, and other relevant documents, (e.g., recruitment advertisements), if applicable, from the IRB/IEC. All correspondence with

the IRB/IEC should be retained in the Investigator File. Copies of IRB/IEC approvals should be forwarded to Pfizer.

9.4. Ethical Conduct of the Study

The study will be conducted in accordance with legal and regulatory requirements, as well as with scientific purpose, value and rigor and follow generally accepted research practices described in Guidelines for Good Pharmacoepidemiology Practices (GPP) issued by the International Society for Pharmacoepidemiology (ISPE), Good Epidemiological Practice (GEP) guidelines issued by the International Epidemiological Association (IEA).

This is a non-interventional study where the 3rd line targeted treatment are prescribed in the usual manner in accordance with the terms of the marketing authorization. There is no assignment of a patient to a particular therapeutic strategy, the treatment decision falls within current practice and the prescription of the medicines is clearly separated from the decision to include the patient in the study. No additional diagnostic or monitoring process is required for participation or during the study. Epidemiological methods shall be used for the analysis of the collected data.

